5.2.5 Echocardiogram/MUGA scan

An echocardiogram or MUGA scan to assess left ventricular ejection fraction (LVEF [%]) will be performed at screening and at the visits indicated in [Table 1](#) and [Table 2](#). The modality of the cardiac function assessments must be consistent within a patient, ie, if an echocardiogram is used for the screening assessment then an echocardiogram should also be used for subsequent scans. The patients should also be examined using the same machine and operator whenever possible. The LVEF value (%) should be recorded on the eCRF.

5.2.6 Vital signs

Vital signs will be performed during Parts A and B, at the times and visits as shown in the Study Plans (see [Table 1](#) and [Table 2](#)). However, the Investigator reserves the right to add extra assessments if there are any abnormal findings or for any other reason the Investigator feels meets this requirement.

Deterioration as compared with baseline in protocol-mandated vital signs should only be reported as AEs if they fulfil any of the SAE criteria or are the reason for discontinuation of treatment with the IP, or the Investigator insists the abnormality should be reported as an AE (see Section [6.3.6](#)).

5.2.6.1 Pulse and blood pressure

Supine blood pressure and pulse rate will be measured as show in the Study Plans (see [Table 1](#) and [Table 2](#)), using a semi-automatic blood pressure recording device with an appropriate cuff size after the patient has been resting in bed for 10 minutes.

5.2.6.2 Body temperature

Body temperature will be assessed at the visits as shown in the Study Plans (see [Table 1](#) and [Table 2](#)), using a semi-automatic body temperature recording device.

5.2.6.3 Weight and height

Height and weight will be assessed at the visits as shown in the Study Plans (see [Table 1](#) and [Table 2](#)). Indoor clothing may be worn but shoes should be removed. For weight assessment, the same weighing scales should be used at each visit.

5.2.7 Other safety assessments

5.2.7.1 Ophthalmologic examination

Full ophthalmic assessment, including slit lamp examination, should be performed at Screening and if a patient experiences any visual symptoms (including blurring of vision), with additional tests if clinically indicated. Ophthalmology examination results at Screening and for additional ophthalmic assessments during Part B should be collected in the eCRF.

Any clinically significant findings, including those confirmed by the ophthalmologist must be reported as an AE. Photographs should be performed to record any clinically significant

findings. These photographs should be available for central review by AstraZeneca and AstraZeneca representatives if necessary.

Patients experiencing corneal ulceration will not be permitted to restart study treatment.

5.3 Other assessments (not applicable)

5.4 Pharmacokinetics

5.4.1 Collection of samples

Venous blood samples for determination of concentrations of AZD9291 and its metabolites (AZ5104 and AZ7550), rifampicin and 4 β -hydroxy-cholesterol in plasma will be taken at the times presented in the Study Plan (Table 1) and the PK sampling schedule (Table 3).

Although every attempt should be made to collect all samples as per the protocol, it is accepted that this will not always be possible and therefore it is essential that the actual time and date of collection of each blood sample (whether collected as per protocol or not) is recorded in the eCRF. Samples will be collected, labelled, stored, and shipped as detailed in the Laboratory Manual.

A 30-minute window will be allowed for samples taken at pre-dose (sample must be taken prior to dose), a 5-minute window will be allowed for post-dose samples up to 1 hour; a 10-minute window for samples taken at 2 to 10 hours post-dose and a 1-hour window for samples taken from 12 hours post-dose onwards. The window for trough samples is ± 1 day; however, on a given day the trough sample must be collected prior to the next dose of IP.

For blood volumes see Section 5.2.2.

5.4.2 Determination of drug concentration

Samples for determination of AZD9291, metabolites (AZ5104 and AZ7550), and rifampicin, in plasma will be analysed by _____ on behalf of Clinical Bioanalysis Alliance, AstraZeneca R&D, using appropriate bioanalytical methods. Samples for determination of 4 β -hydroxy-cholesterol in plasma will be analysed by _____ on behalf of AstraZeneca R&D, using appropriate bioanalytical methods.

Full details of the analytical method used will be described in separate bioanalytical reports. All samples still within the known stability of the analytes of interest at the time of receipt by the bioanalytical laboratory will be analysed.

In addition, the PK samples may be subjected to further analyses by AstraZeneca in order to further investigate the presence and/or identity of additional AZD9291 metabolites. Any results from such analyses will be reported separately from the Clinical Study Report (CSR).

Details on sample processing, handling, shipment and storage are provided in the Laboratory Manual.

5.4.3 Storage and destruction of pharmacokinetic samples

Pharmacokinetic samples will be disposed of after the Bioanalytical Report finalisation or 6 months after issuance of the draft Bioanalytical Report (whichever is earlier), unless requested for future analyses.

Incurred sample reproducibility analysis, if any, will be performed alongside the bioanalysis of the test samples. The results from the evaluation will not be reported in the CSR but separately in a Bioanalytical Report.

Any residual PK samples may be used for future exploratory biomarker research (in this case, residual back-up PK samples will be retained at AstraZeneca or its designee; see details in the Laboratory Manual).

5.5 Pharmacodynamics (not applicable)

5.6 Pharmacogenetics

If a patient agrees to participate in the optional pharmacogenetics research component of the study a blood sample will be collected (see [Table 1](#)).

AstraZeneca may perform genetic research in the AZD9291 clinical pharmacology development programme to explore how genetic variations may affect the clinical PK of AZD9291.

For this clinical study pharmacogenetic research will be limited to analysis of genes that may affect AZD9291 PK (for example, but not limited to, drug metabolising enzymes and drug transporters) and will be performed if the results from the clinical study cannot be explained by the current level of drug metabolism and PK understanding or if patients with outlying PK behaviour are observed.

The results of this pharmacogenetic research will be reported separately and will not form part of the CSR.

5.6.1 Collection of pharmacogenetic samples

The patient's consent to participate in the pharmacogenetic research components of the study is mandatory.

The single blood sample for genetic research will be obtained from the patients at Visit 2 (Day -1 or Day 1) prior to the first administration of AZD9291 in the study. Although genotype is a stable parameter, early sample collection is preferred to avoid introducing bias through excluding patients who may withdraw due to an AE, such patients would be important to include in any genetic analysis. If for any reason the sample is not drawn at Day -1, it may be taken at any visit until the last study visit. Only one sample should be collected per patient for genetics during the study.

Samples will be collected, labelled, stored and shipped as detailed in the Laboratory Manual.

5.6.2 Storage, re-use and destruction of pharmacogenetic samples

The processes adopted for the coding and storage of samples for genetic analysis are important to maintain patient confidentiality. Samples will be stored for a maximum of 15 years from the date of the Last Patient's Last Visit, after which they will be destroyed. Deoxyribonucleic acid (DNA) is a finite resource that may be used up during analyses. The results of any further analyses will be reported separately in a scientific report or publication.

For all samples, irrespective of the type of coding used, the DNA will be extracted from the blood sample. The DNA sample will be assigned a unique number replacing the information on the sample tube. Thereafter, the DNA sample will be identifiable by the unique DNA number only. The DNA number is used to identify the sample and corresponding data at the AstraZeneca genetics laboratories, or at the designated contract laboratory. No personal details identifying the individual will be available to any person (AstraZeneca employee or contract laboratory staff working with the DNA).

The samples and data for genetic analysis in this study will be single coded. The link between the patient enrolment code and the DNA number will be maintained and stored in a secure environment, with restricted access within the relevant tracking system at AstraZeneca. The link will be used to identify the relevant DNA samples for analysis, facilitate correlation of genotypic results with clinical data, allow regulatory audit, and to trace samples for destruction in the case of withdrawal of consent when the patient has requested disposal/destruction of collected samples not yet analysed.

5.7 Biomarker analysis (not applicable)

6. SAFETY REPORTING AND MEDICAL MANAGEMENT

The PI is responsible for ensuring that all staff involved in the study are familiar with the content of this section.

6.1 Definition of adverse events

An AE is the development of an undesirable medical condition or the deterioration of a pre-existing medical condition following or during exposure to a pharmaceutical product, whether or not considered causally related to the product. An undesirable medical condition can be symptoms (eg, nausea, chest pain), signs (eg, tachycardia, enlarged liver) or the abnormal results of an investigation (eg, laboratory findings, ECG). In clinical studies, an AE can include an undesirable medical condition occurring at any time, including run-in or washout periods, even if no study treatment has been administered.

The term AE is used to include both serious and non-serious AEs.

6.2 Definitions of serious adverse event

A SAE is an AE occurring during any study phase (ie, run-in, treatment, washout, follow-up), that fulfils one or more of the following criteria:

- Results in death
- Is immediately life-threatening
- Requires in-patient hospitalisation or prolongation of existing hospitalisation
- Results in persistent or significant disability/incapacity or substantial disruption of the ability to conduct normal life functions
- Is a congenital abnormality or birth defect
- Is an important medical event that may jeopardise the patient or may require medical intervention to prevent one of the outcomes listed above.

For further guidance on the definition of a SAE, see [Appendix B](#) to the Clinical Study Protocol.

6.3 Recording of adverse events

6.3.1 Time period for collection of adverse events

Adverse Events will be collected from the time of signature of informed consent, throughout the Part A treatment periods, Part B, and the follow-up period.

All SAEs will be recorded from the time of informed consent.

Patients entering Part B will be able to continue taking AZD9291 for as long as they are receiving clinical benefit; however study assessments will cease approximately 12 months after the last patient enters Part B. After Part B, there may be some patients remaining on study treatment via the continued access part of this protocol. For these patients who are continuing to receive AZD9291 and being followed as part of routine clinical care, AstraZeneca will collect limited information only (see Section 7.8).

6.3.2 Follow-up of unresolved adverse events

Any AEs that are unresolved at the patient's last AE assessment or other assessment/visit as appropriate in the study will be followed up by the Investigator for as long as medically indicated, but without further recording in the eCRF. AstraZeneca retains the right to request additional information for any patient with ongoing AE(s)/SAE(s) at the end of the study, if judged necessary.

If an Investigator learns of any SAEs, including death, at any time and he/she considers there is a reasonable possibility that the event is related to AZD9291, the Investigator should notify AstraZeneca.

6.3.3 Variables

The following variables will be collected for each AE;

- AE (verbatim)
- The date and time when the AE started and stopped
- Changes in CTCAE grade (for skin reactions and diarrhoea only); maximum CTCAE grade for all other AEs
- Whether the AE is serious or not
- Investigator causality rating against the IP and other study drug (ie, rifampicin) (yes or no)
- Action taken with regard to IP
- Outcome.

In addition, the following variables will be collected for SAEs:

- Date AE met criteria for serious AE
- Date Investigator became aware of serious AE
- AE is serious due to
- Date of hospitalisation
- Date of discharge
- Probable cause of death
- Date of death
- Autopsy performed
- Causality assessment in relation to Study procedure(s)
- Causality in relation to other medication
- Description of AE.

It is important to distinguish between serious and severe AEs. Severity is a measure of intensity whereas seriousness is defined by the criteria in Section 6.2. An AE of severe intensity need not necessarily be considered serious. For example, nausea that persists for several hours may be considered severe nausea, but not a SAE unless it meets the criteria shown in Section 6.2. On the other hand, a stroke that results in only a limited degree of disability may be considered a mild stroke but would be a SAE when it satisfies the criteria shown in Section 6.2.

The grading scales found in the revised CTCAE version 4 will be utilised for all events with an assigned CTCAE grading. For those events without assigned CTCAE grades, the recommendation in the CTCAE criteria that converts mild, moderate and severe events into CTCAE grades should be used. A copy of the CTCAE version 4 can be downloaded from the Cancer Therapy Evaluation Program website (<http://ctep.cancer.gov>).

6.3.4 Causality collection

The Investigator will assess causal relationship between IP and each AE, and answer ‘yes’ or ‘no’ to the question ‘Do you consider that there is a reasonable possibility that the event may have been caused by the investigational product?’.

For SAEs causal relationship will also be assessed for other medication and study procedures and additional study drug (rifampicin). Note that for SAEs that could be associated with any study procedure the causal relationship is implied as ‘yes’.

A guide to the interpretation of the causality question is found in [Appendix B](#) to the Clinical Study Protocol.

6.3.5 Adverse events based on signs and symptoms

All AEs spontaneously reported by the patient or care provider or reported in response to the open question from the study personnel: ‘Have you had any health problems since the previous visit/you were last asked?’, or revealed by observation will be collected and recorded in the eCRF. When collecting AEs, the recording of diagnoses is preferred (when possible) to recording a list of signs and symptoms. However, if a diagnosis is known and there are other signs or symptoms that are not generally part of the diagnosis, the diagnosis and each sign or symptom will be recorded separately.

6.3.6 Adverse events based on examinations and tests

The results from protocol mandated laboratory tests and vital signs will be summarised in the CSR. Deterioration as compared to baseline in protocol-mandated parameters should therefore only be reported as AEs if they fulfil any of the SAE criteria or are the reason for discontinuation of treatment with the IP, unless clearly due to progression of disease under study (see Section 6.3.8).

If deterioration in a laboratory value/vital sign is associated with clinical signs and symptoms, the sign or symptom will be reported as an AE and the associated laboratory result/vital sign will be considered as additional information. Wherever possible the reporting Investigator

uses the clinical, rather than the laboratory term (eg, anaemia versus low haemoglobin value). In the absence of clinical signs or symptoms, clinically relevant deteriorations in non-mandated parameters should be reported as AE(s).

Deterioration of a laboratory value, which is unequivocally due to disease progression, should not be reported as an AE/SAE.

Any new or aggravated clinically relevant abnormal medical finding at a physical examination as compared with the baseline assessment will be reported as an AE.

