^b Day 1 is the day of dosing; Day -1 is the day before dosing. All Day -1 procedures must be performed on Day -1 or pre-dose on Day 1 provided the results are reviewed before dosing. If the patient has been screened within 48 hours of Day 1, safety laboratory tests (haematology, coagulation, biochemistry and urinalysis) do not need to be repeated.

^c Patients will check into the clinic on the morning of Day 28, Day 49 and Day 77 and be prepared to stay overnight for 24 hours serial blood collections and safety assessments.

^d Height to be assessed at Screening only. Weight to be assessed at all timepoints; the same weighing scales should be used at each visit. For height and weight, indoor clothing may be worn but shoes should be removed.

^e Supine BP and pulse will be measured pre-dose, using a semi automatic BP recording device with an appropriate cuff size after the patient has been resting in bed for 10 minutes. For ECG, patients will rest at least 10 minutes before the start of each ECG recording and they must be in the same supine (maximum 30 degrees flexion in the hip and feet not in contact with the footboard) body position at each recording timepoint. On Days 28, 49 and 77, assessments will be performed pre-dose and at 3, 6 and 12 hours post-dose.

- ^f For haematology and clinical chemistry tests, see [Table 4](#). Coagulation (aPTT and INR) will be performed at Screening and if clinically indicated. For patients taking warfarin reference Section [7.7](#).
- ^g Protein, blood and glucose; microscopic analysis is to be performed if required.
- ^h Pre-menopausal women of childbearing potential must have a negative urine or serum pregnancy test within 28 days prior to starting treatment and a confirmatory test before treatment at Visit 1. In the event of suspected pregnancy during the study, the test should be repeated and, if positive, the patient discontinued from study treatment immediately. Pregnancy test will be repeated at the follow-up 30 (± 7) days after last dose of study medication.
- ⁱ Patients will be invited to participate in optional genetic research. The patient must provide separate informed consent. If the patient declines to consent to the optional genetic research, this will not exclude the patient from participating in any other aspect of the study.

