- ^j Patients will take AZD9291 80 mg once daily fasted from Day 1 to Day 77. Doses on Day 28, Day 49, and Day 77 will be administered at the clinic by clinic personnel. AZD9291 will be administered fasted from at least 2 hours before dosing to at least 2 hours after dosing. The study treatments should be swallowed whole with approximately 240 mL of water, and not chewed, crushed, dissolved or divided. On Days 28, 49, and 77, water can be allowed as desired except for 1 hour before and after AZD9291 administration. On all other study days there are no water restrictions. The same fasting restrictions apply to self-administered doses.
- ^k Patients will take 600 mg rifampicin once daily from Day 29 to Day 49. In Period 2, doses from Day 29 until Day 48 will be self-administered by the patients. The doses on Day 49 (Period 2 Day 21) will be administered at the clinic by clinic personnel. All rifampicin doses should be taken fasted from at least 2 hours before dosing to at least 2 hours after dosing.
- ^l AZD9291 PK samples will be collected at the times specified in [Table 3](#).
- ^m Rifampicin PK samples will be collected at the times specified in [Table 3](#).
- ⁿ If a patient withdraws for any reason, any ongoing study-related toxicity or SAE at discontinuation must be monitored until resolution. After discontinuation from treatment, patients must be followed up for any new AEs for 30 calendar days after the last dose of study drug. Any existing and any new AEs occurring during the 30-day period must be recorded and followed to resolution if possible.
- ^o Brief physical examination (including general appearance, skin, abdomen, cardiovascular system, and lungs).

AE adverse event; aPTT activated partial thromboplastin time BP blood pressure; C check diary; ECG electrocardiogram; ECOG Eastern Cooperative Oncology Group; HBV Hepatitis B; HCV Hepatitis C virus; INR international normalised ratio; IP investigational product; MUGA multiple gated acquisition scan; P provide diary; PK pharmacokinetics; SAE serious adverse event

Table 2 Study Plan – Part B

Visit Number/Day	Visit 13, Day 77, Part A ^a	Visit 101/Day 84	Visit 102/Day 91	Visit 103/Day 98	Visit 104/Day 105	Subsequent on-treatment visits every 4 weeks ^b Visit 105 onwards Day 1 of next visit period (Equals Day 133 [Week 19] etc)	Follow-up 30 (±7) days after IP permanently discontinued in Part B ^c
Visit window		±3d	±3d	±3d	±3d	±7d	±7d
Physical examination ^d		X	X	X	X	X	X

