Pre-menopausal women of childbearing potential must have a negative urine or serum pregnancy test within 28 days prior to starting study treatment, and a confirmatory test before treatment at Visit 1. In the event of suspected pregnancy during the study, the test should be repeated and, if positive, the patient discontinued from study treatment immediately. The pregnancy test will be repeated at follow-up 30 (±7) days after last dose of study medication (in Part A or Part B as appropriate). Tests will be performed by the hospital's local laboratory. If results are positive, the patient is ineligible/must be discontinued from the study.

Routine urinalysis should be performed if clinically indicated. Microscopic analysis should be performed by the hospital's local laboratory if required.

Any clinically significant abnormal laboratory values should be repeated as clinically indicated and recorded on the eCRF.

NB. In case a patient shows an AST **or** ALT ≥ 3 x ULN **or** total bilirubin ≥ 2 x ULN please refer to [Appendix E](#) ‘Actions required in cases of combined increase of Aminotransferase and Total Bilirubin – Hy’s Law’, for further instructions.

The Investigator should make an assessment of the available results with regard to clinically relevant abnormalities. The laboratory results should be signed and dated and retained at centre as source data for laboratory variables. For information on how AEs based on laboratory tests should be recorded and reported, see Section 6.3.

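### Two Part A adverse-event recording rules overlook rifampicin: Section 6.3.6 recognises laboratory AEs only through SAE criteria or stopping the IP, and Sections 6.3.3 and 6.3.4 differ on rifampicin causality for non-serious AEs

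*Protocol*

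**What the plan says.** The synopsis and Sections 7.1 and 7.1.1 of the protocol identify AZD9291 as the IP and list rifampicin apart from it, as an additional study drug. Table 1, footnote k, makes rifampicin part of Period 2 for everyone: "Patients will take 600 mg rifampicin once daily from Day 29 to Day 49".

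**Laboratory and vital-sign AEs.** Section 6.3.6 explains that mandated laboratory and vital-sign results go into the study report, and that worsening results may "therefore only be reported as AEs if they fulfil any of the SAE criteria or are the reason for discontinuation of treatment with the IP", with an exception for clear disease progression. Section 5.2.1 gives no separate rule for laboratory tests: "For information on how AEs based on laboratory tests should be recorded and reported, see Section 6.3". Section 5.2.6 repeats the rule for vital signs but adds a third route: "or the Investigator insists the abnormality should be reported as an AE".

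**Causality.** Section 6.3.3 lists, among the variables to be collected for every AE, "Investigator causality rating against the IP and other study drug (ie, rifampicin) (yes or no"). Section 6.3.4 opens with "The Investigator will assess causal relationship between IP and each AE" and then adds: "For SAEs causal relationship will also be assessed for other medication and study procedures and additional study drug (rifampicin"). The action-taken item in Section 6.3.3 refers to the IP alone.

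**Use of the data.** Section 2.3 sets a Part A objective on the safety of AZD9291 with and without rifampicin. Section 8.5.3 plans counts of AEs after AZD9291 and rifampicin, and summaries of treatment-related AEs by part and by period within part.

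**The concern.** These recording rules read as if there were one study drug, but Part A has two. If a laboratory change leads a patient to stop rifampicin while AZD9291 continues, Section 6.3.6 does not make that change an AE. The same change would be an AE if it ended AZD9291. A finding that ended a mandated study drug could therefore be absent from the Period 2 AE counts, which are what bears on tolerability during co-administration.

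The causality sections raise a different problem. Sites are told in one place to rate rifampicin for each AE, and in the next are asked for it only under serious events. With about 16 sites, attribution of non-serious AEs to rifampicin could be missing or uneven. An analysis plan cannot restore a rating that was never collected.

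**Working it through.** The protocol states no figure on this point that could be reproduced. The check is a comparison of text, plus some counting from Table 1.

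**1. Can the term IP cover rifampicin?** No. The synopsis and Sections 7.1 and 7.1.1 separate the two drugs, and Sections 6.3.3 and 6.3.4 name rifampicin next to the IP as something else.

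**2. Can rifampicin end while AZD9291 continues?** Yes. Section 3.3 allows a patient who leaves Part A early to continue AZD9291 in Part B, where rifampicin is not given.

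**3. Which routes make a mandated laboratory deterioration an AE?**

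| Route | Source | Covers a non-serious, symptom-free change that ends rifampicin only? |
|---|---|---|
| Meets an SAE criterion | 6.3.6 | No, by definition of the case |
| Reason for stopping the IP | 6.3.6 | No, AZD9291 continues |
| Associated sign or symptom | 6.3.6 | No, there is none |
| Relevant change in a non-mandated parameter | 6.3.6 | No, the test is mandated |
| Investigator insists | 5.2.6 | No, vital signs only |

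A recorded diagnosis would still be an AE. What is left uncovered is a laboratory value alone.

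**4. When could it arise?** The scheduled on-treatment chemistry and haematology draws in Table 1 are Days 7, 14, 21, 28, then 35, 42, 49, then 56, 63, 70, 78: 4 + 3 + 4 = 11. Three fall within rifampicin dosing (Days 29 to 49, 21 doses). If rifampicin stops from the day after the draw, the doses left untaken are:

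- Day 35: 49 − 35 = 14
- Day 42: 49 − 42 = 7
- Day 49: 49 − 49 = 0

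So 2 of 11 scheduled draws (18%), plus any unscheduled tests, can lead to an early rifampicin stop.

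**5. Vital signs.** Table 1 schedules blood pressure and pulse in Period 2 on Day 49 only; footnote e reads "On Days 28, 49 and 77, assessments will be performed pre-dose and at 3, 6 and 12 hours post-dose". Day 49 is the last rifampicin day, and Section 5.2.6 gives the investigator an override. In practice the gap concerns laboratory tests.

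**6. Causality, side by side.**

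| | Non-serious AE | Serious AE |
|---|---|---|
| 6.3.3, IP | collected | collected |
| 6.3.3, rifampicin | collected | collected |
| 6.3.4, IP | asked | asked |
| 6.3.4, rifampicin | not mentioned | asked |

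The sections differ in one cell. A site that satisfies both collects the rifampicin rating for every AE. Data are lost only where 6.3.4 is read alone.

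**7. Largest effect on an incidence.** One patient out of the numerator changes a Period 2 incidence by at most 1/38 = 2.6 percentage points if all 38 planned patients are in the denominator, or 1/30 = 3.3 points if 30 patients reach Period 2. The change is zero if that patient has another AE in the same tabulated category.

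The protocol gives no rate for laboratory changes that end rifampicin, and none is assumed. The 105/174 (60%) in Section 1.3 counts patients with any AE in a Phase I study of AZD9291, so it does not measure this.

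**The case against.** The strongest reply is that almost everything is recorded somewhere.

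- Section 6.3.6 limits laboratory AEs because the values are summarised in the report anyway, and Section 8.5.3 adds shift tables for selected tests and flagged listings.
- Section 5.2.1 has clinically significant abnormal values repeated and entered on the eCRF.
- Section 3.9.1 asks for the date of, and reasons for, stopping study drug, although under a heading about the IP. Sections 7.2.1 and 7.5 record dosing changes and administration.
- Appendix E, section 3, requires sponsor notification and prompt entry of liver values that reach its thresholds, even in isolation. Section 6.3.7 notes that such cases may need reporting as SAEs.
- The important-medical-event criterion in Section 6.2 may capture some of the rest.

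All of this stands, and it makes the gap narrow. None of it makes the remaining change an AE, so none of it brings that change into the AE counts.

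On causality, the reply is that Section 6.3.3 is the explicit collection list, that Section 9.4 provides for queries on missing data, and that Section 8.5.3 does not say which drug treatment-related refers to and leaves detail to the SAP. This also largely stands. A reader might infer that Section 6.3.4 restricts rifampicin causality to SAEs. The text does not support that: it adds rifampicin for SAEs and nowhere excludes it for other events. The sections are mismatched, but both can be followed.

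A reader might also infer that laboratory safety signals on rifampicin go unseen. The recording routes above do not support that either.

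**Conclusion.** The point holds in a limited form. As written, a non-serious, symptom-free deterioration in a mandated laboratory test that ends rifampicin while AZD9291 continues is not recorded as an AE, and the action-taken item would not show the rifampicin stop. Separately, the two causality sections are not aligned for non-serious AEs, which matters only at sites that rely on Section 6.3.4 alone.

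The 2.6 to 3.3 points per omitted patient are a ceiling. They assume a Period 2 denominator of 30 to 38. It would be wrong to read them as the loss for every omitted patient, because another AE in the same category removes the effect.

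The conclusion rests on sites applying Section 6.3.6 literally and on IP meaning AZD9291 alone, as the protocol defines it. How the eCRF presents the causality item cannot be seen here. Only Part A safety data are touched; no pharmacokinetic result, treatment rule or monitoring step changes. This is a worthwhile clarification, not a flaw that threatens the study.

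**What to change.** Three wording changes bring the sections into line:

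1. Section 6.3.6: extend the discontinuation trigger to the IP *or, in Part A, rifampicin*. Use the same words in Section 5.2.6, for consistency only.
2. Section 6.3.3: extend the action-taken item to the IP *and, in Part A, rifampicin*, so that an AE record can show that rifampicin was stopped.
3. Section 6.3.4: require causality against the IP for each AE, and against rifampicin for each Part A AE starting on or after the first rifampicin dose. Write the same scope into Section 6.3.3, which now says each AE without a time limit; otherwise the two sections would still disagree.

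Appendix E can stay as it is. No visits, samples or staff are added, and the rifampicin causality item is already listed in 6.3.3. The cost is a few more laboratory-based AEs in Part A, plus one more causality answer and one more action-taken answer per AE from Period 2 onwards.
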